Here we propose to quantify the effect of the HWA on walking at the knee, ankle, trunk and arm segments during phases of the gait cycle (GC) as described by Perry. (Perry & Davids, 1992) Additionally, we will quantify the aftereffect of HWA use in these joints and segments. Quantification will include measurement of walking kinematics (joint angles), muscle activity (EMG output), ground reaction forces and Spatiotemporal gait characteristics measured in three conditions: 1) Walking at self-selected pace (control), 2) walking with the HWA (4Nm assist), 3) and immediately following HWA walking (aftereffect). Our overall hypothesis is that walking with the HWA in the (hip flexion and extension) assist mode results in reallocation of cortical motor resources to the knee, ankle, trunk and arm. We also propose that normalizing walking through optimization (activation of latent residual capacity) of previously non-optimized corticospinal motor units with the HWA will produce a short-term (or within-session) aftereffect. We hypothesize that aftereffect will be greater in individuals with less lower extremity use since their stroke. Therefore we will characterize lower extremity use by quantifying the average number of steps each participant takes using an activity monitor.

Background of the device:

The Honda Walking Assist (HWA) System (pictured below) is a robotic device developed by Honda R&D Corporation ®, Japan (https://world.honda.com/Walking-Assist/). It is controlled through software run on a tablet. The device weights 2.7 kgs and has two brushless motors that run on a lithium ion battery with an approximate running time of 60 minutes. It comes in 2 sizes with adjustable frames making it possible to fit a variety of body types/sizes.

It takes approximately 5 minutes to fit the HWA on to the user. It's computer-activated motors use hip angle information to guide assistance delivered through the thigh straps to the legs in time with the walking cycle. The maximum torque delivered is 4 Nm. Wearers have described this level of assistance as "mild" to "moderate". The goal of device use is to promote walking ease by increasing stride length and improving the step symmetry.

Honda began leasing the HWA in Japan in 2015, in January of 2018 they obtained medical device approval in the European Union. Food and Drug administration approval of the HWA in the United States is in process at this time.

Study Objectives:

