- 9. (If applicable) ≥ 90 days post major orthopedic surgery (such as a joint replacement)
- 10. (If applicable) ≥ 6 months post cardiac surgery

[figure not shown]
Exclusion criteria

- Serious cardiac conditions (hospitalized for myocardial infarction or heart surgery within 3 months, congestive heart failure, unstable cardiac arrhythmias, hypertrophic cardiomyopathy, severe aortic stenosis, angina or dyspnea at rest or during activities of daily living)
- 2. Severe arthritis or orthopedic conditions that limit lower extremity range of motion (> 10° or < 90° knee flexion, lacking > 25° hip extension, >15° from neutral plantar flexion.)
- 3. Preexisting neurologic disorders such as Dementia, Multiple Sclerosis, Amyotrophic Lateral Sclerosis, Parkinson's Disease or Ataxia.
- 4. History of lower limb amputation, non-healing ulcers, legal blindness or severe visual impairment

Testing Plan:

Enrolled participants will be pseudo-randomized by drawing from an envelope into either Group A or Group B and scheduled for two testing sessions 1-week ± 3 days apart. Demographic interview, MoCA, Biometrics and StepWatch activity monitor instruction will be conducted on the first testing day for participants in both groups. Group A participants will complete measures in Data Set 2 during the initial

testing session and Data Set 3 during the final testing session. Group B participants will complete measures in Data Set 3 during the initial testing session and Data Set 2 during the final testing session.

[figure not shown]

Each testing sessions will be approximately 2.5 to 3 hours in length. The estimated time for each measure or procedure is indicated in the table below. (data collection forms are attached)

		Time
	Measure or procedure	estimate
	*	(minutes)

	Total time	~2 hours, 5 minutes	
Data Set #3	Kinematic and EMG data collection during walking (see detailed schematic below)	30	
	Set-up of 40 motion capture markers and 16 EMG electrodes on participants body	90	
	Collect StepWatch from participants (Group A)	5	
	Total time	~1 hour 50 min	
Data Set #2	HWA Stair climbing Ascend /Descend test (1st for grp B)	15	
	Activities-Specific Balance Confidence Scale	10	
	Control Stair climbing Ascend/Descent test (1st for grp A)	15	
	Biometrics, EMG and HWA set-up for stairs	30	
	Lower extremity Fugl-Meyer (motor recovery)	10	
	Modified Tardieu Scale (muscle tone)	10	
	Somatosensory testing	5 15	
	Collect StepWatch from participants (Group B)		

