In the case that a participant, for any reason, does not complete the study the following categories will be used to record the occurrence:

- 1. Patient withdraws
- 2. Patient is unable to perform protocol requirements
- 3. Patient demonstrates a change in medical condition
- 4. Patient experiences an adverse event that makes continuation in the protocol unsafe
- 5. PI determines that continuation in the study would not be appropriate
- 6. Other

Study Risks:

This is a study of walking performance therefore risk of falling is present. This risk is similar
to the risk one would undertake while participating in outpatient physical therapy for walking
training following stroke. It will be mitigate by study personnel maintain contact with the
participant during walking, transitions and stair climbing. Participants will be encouraged to

- wear their most comfortable walking shoes and will be walking in a well-lit, open environment.
- 2. While the adhesive materials used in this study are latex free, the risk of skin irritation is present. Skin irritation could arise from the tape used to fix the motion capture markers, the EMG sensors or from the HWA device itself rubbing on the skin. This risk will be discussed with the participants during the process of obtaining informed consent and they will be instructed to inform study personnel if they experience itching or irritation. Participants who demonstrate somatosensory impairment may not feel skin irritation. Those participants will receive a visual skin check in areas of possible irritation midway through the assessments. Adjustments to the size and fitting of the HWA will be conducted to address skin irritation including the possibility of adding additional padding or other measures to reduce irritation.
- The HWA device delivers a maximum 4 Nm of torque to the legs during walking. There is a
 chance that the device could malfunction during use, which could cause a loss of stability or
 balance. To mitigate this risk study personnel will maintain contact with study participants
 during device use.
- 4. There is a possible risk that study participants may develop muscle soreness from the walking or stair climbing they will perform in as part of the assessments. To mitigate this risk participants will be given scheduled rest periods during the protocol and allowed to take additional rest if they choose.

Statistical considerations and Data Management

Study design

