This study has a within-subjects design in which walking parameters including kinematics and muscle activity will be collected from participants during two testing sessions. For practical reasons a non-probability sample will be used. Pseudo randomization of participants into two groups will be used to control, in part, for the effect of order of testing on study outcomes.

Sample Size

The sample size for this study was calculated based on the assumption of detecting a meaningful difference in peak knee flexion angle (primary hypothesis) between the control and HWA walking conditions. To detect a mean difference of 5 degrees with a standard deviation of 5 degrees using a two-sided test and significance level of 5%, power of 80%, would require 10 participants. To allow for a 20% dropout rate 12 participants will be recruited. At the mid point of participant testing (6 participants) sample size will be recalculated and the sample adjusted if necessary to achieve appropriate power for the primary aims.

Data analysis plan

The measures collected for each subject in each condition will be compared within and across participants using paired t-tests and ANOVA. The alpha level will be set at p<0.05 to indicate statistical significance.

Data Management

Participant data collected in this study will be kept completely confidential and in compliance with HIPPA requirements. Participants will be assigned a study ID, all data collection forms and tools will use study ID therefore data will be de-identified. Data will be stored in locked cabinets, electronic data will be kept on secure, password protected computers. Data will be retained securely for three years after study publication.

References

- Botner, E. M., Miller, W. C., & Eng, J. J. (2005). Measurement properties of the Activities-specific Balance Confidence Scale among individuals with stroke. *Disability and rehabilitation*, 27(4), 156-163.
- Flansbjer, U.-B., Holmbäck, A. M., Downham, D., Patten, C., & Lexell, J. (2005). Reliability of gait performance tests in men and women with hemiparesis after stroke. *Journal of Rehabilitation Medicine*, *37*(2), 75-82.

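### The aftereffect-versus-control walking contrast is confounded with time in session, and the A/B draw does not correct it

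*Combined protocol and SAP*

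**What the plan says.** Under Statistical considerations and Data Management, the Study design paragraph gives the purpose of the two groups: "Pseudo randomization of participants into two groups will be used to control, in part, for the effect of order of testing on study outcomes".

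The Testing Plan shows what the draw changes:

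- **Session order.** "Group A participants will complete measures in Data Set 2 during the initial" session and Data Set 3 in the final one; "Group B participants will complete measures in Data Set 3 during the initial testing session and Data Set 2 during the final testing session".
- **Stair-test order.** The procedure table has "Control Stair climbing Ascend/Descent test (1st for grp A") and "HWA Stair climbing Ascend /Descend test (1st for grp B").

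Walking appears in that table as a single 30-minute entry in Data Set 3, "Kinematic and EMG data collection during walking (see detailed schematic below"), with no group label. The schematic itself is not shown in the text available. The Background and rationale lists the walking measurements as "measured in three conditions: 1) Walking at self-selected pace (control), 2) walking with the HWA (4Nm assist), 3) and immediately following HWA walking (aftereffect").

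The hypotheses under Aims I and II repeatedly name the after-assist condition. The StepWatch item in the description of measures says that Aims 1 and 2 look for a difference between control and aftereffect. The Data analysis plan specifies paired t-tests and ANOVA at the 5% level and mentions no term for order or time in session. Study Risks provides that "participants will be given scheduled rest periods during the protocol and allowed to take additional rest if they choose".

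**The concern.** In a within-subject study each participant is their own control, so anything that changes over the session along with the condition is counted as a condition effect. People 12 weeks to 1 year after stroke may walk differently later in a session because they have warmed up, become used to the markers and walkway, or tired. If the aftereffect is measured late and its control early, a gain from warm-up would be read as an HWA aftereffect, and fatigue could hide a real one.

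This contrast carries much of the scientific argument. It is the one measured without device torque, so it bears most directly on the claim that motor resources have been reallocated. A reader of the Study design sentence could reasonably believe that order effects on it have been dealt with.

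**Working it through.** **Step 1: does the draw reach the walking conditions?**

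| Element | Differs between groups A and B? | Source |
|---|---|---|
| Visit holding the walking data | Yes | Testing Plan |
| Control or HWA stair test first | Yes | Testing Plan table |
| Order of control, HWA and aftereffect walking within Data Set 3 | No difference stated; schematic not shown | Testing Plan table |

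Swapping visits moves the whole walking block by about a week and leaves the order inside it unchanged.

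**Step 2: could the order be balanced for the aftereffect?** By definition this condition follows HWA walking. The Background and rationale also hypothesises a within-session aftereffect, so a control walk done after the HWA in the same session could be contaminated by it. A clean control has to precede the HWA, and the aftereffect has to come after it. Condition and time are then aligned in both groups, and no order term in a model could separate them.

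**Step 3: reproduce the plan's own figure.** Inputs from Sample Size: difference 5 degrees, SD 5 degrees, two-sided 5%, power 80%, 10 participants. For a paired t-test with true mean difference δ and SD of differences s:

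- noncentrality λ = δ√n / s, with n − 1 degrees of freedom;
- rejection probability = P(|T| > t(0.975, n − 1)), where T is noncentral t with noncentrality λ.

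With n = 10, λ = 5 × √10 / 5 = 3.16 and power is 80.3%; with n = 9 it is 74.8%. The stated 10 is reproduced, provided that 5 degrees is the SD of the paired differences. The plan recruits 12 to allow for 20% dropout (12 × 0.8 = 9.6, about 10 completers), so both sizes are shown below.

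**Step 4: drift with no HWA effect.** In a fixed order a drift d adds one-for-one to the contrast, so δ is replaced by d. The drift sizes are assumptions.

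| Assumed drift | λ, n=10 | Declared significant, n=10 | λ, n=12 | Declared significant, n=12 |
|---|---|---|---|---|
| 0 | 0 | 5.0% | 0 | 5.0% |
| 1 degree | 0.63 | 8.8% | 0.69 | 9.7% |
| 2 degrees | 1.26 | 20.5% | 1.39 | 24.5% |
| 2.5 degrees | 1.58 | 29.3% | 1.73 | 35.3% |

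A larger sample raises these rates, so an increase at the planned midpoint recalculation would not help.

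**Step 5: would a formal drift-corrected test be a practical remedy?** Split the control passes into early and late blocks and test (after − late) − (late − early) = after − 2 × late + early. With equal, independent block errors of variance σ², this has variance (1 + 4 + 1)σ² = 6σ², against 2σ² for a simple paired difference. The SD rises by √(6/2) = √3, from 5 to 8.66 degrees. Power for a true 5-degree effect is then about 37% at n = 10 (λ = 1.83) and 45% at n = 12 (λ = 2.00), compared with 80% and 88% for the plain paired test. Drift is therefore better handled as a sensitivity analysis than as a hurdle in the main test.

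**The case against.** The strongest reply is that the order, number and repetition of walking passes would be set out in the schematic, which is not available here. A repeated control walk or a group-specific order of control and HWA cannot be excluded. This stands. A reader might infer that control comes first for every participant, that no device-free reference walking is planned, or that HWA versus control is confounded too. The text supports these only through the order in which the conditions are listed, and none can be stated as fact.

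A reader might also infer that the claimed order control is absent for all walking outcomes. That goes too far. The draw balances which visit holds the walking data, and with it exposure to HWA stair climbing at a visit about a week before. The Study design sentence claims control only in part, so what it needs is clarification.

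It is also fair to say that:

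- a fixed order has good reason behind it, given the expected carryover;
- exposure is modest, at about 12 minutes of walking (296 m at 0.4 m/s = 740 s, or 12.3 minutes) with rests;
- fatigue would more plausibly work against the hypothesised gains;
- the 5-degree SD is given for control versus HWA in peak knee flexion, not for the aftereffect contrast.

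These points limit the size of the concern. Rests may reduce fatigue but do not remove warm-up or practice. None of the points separates the aftereffect from time in session.

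**Conclusion.** The concern holds for the aftereffect-versus-control contrast. On the visible text that contrast is confounded with time in session, the A/B draw cannot correct this, and the planned paired analysis cannot separate the explanations. For HWA versus control the same may be true, but that depends on the schematic and is left open.

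The size is illustrative. With 10 to 12 participants, drifts of 1 to 2.5 degrees would inflate a nominal 5% error rate to between about 9% and 35%. This rests on three assumptions: no HWA effect, an SD of 5 degrees carried over from another contrast, and drift sizes that the documents do not supply. The sample-size calculation is not in question. This is a limitation to state and probe, and it does not call for a redesign.

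**What to change.** Keep the order of conditions, the number of passes, and the mean of all control passes as the main comparator. Then:

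1. Record the order of every walking pass.
2. Pre-specify a sensitivity analysis reporting, with confidence intervals, (a) the late-minus-early change within the control passes, as device-free drift; (b) the aftereffect against the late control passes; and (c) early against late post-HWA passes.
3. Pre-specify the interpretation: if the aftereffect is not clearly larger than the drift, report it as a within-session change and not as an effect of the HWA.
4. In the Study design paragraph, state that the A/B groups balance session order and stair-test order, and that the aftereffect contrast is not balanced for time in session. State the walking order in the text as well as in the schematic.

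The cost is protocol wording, labelling of passes and a little more analysis, with no extra walking, visits or participants. Drift estimates will be imprecise with about 10 to 12 participants. Drift during the HWA block itself, including donning and doffing, is not measured. A fading or persisting pattern in (c) is suggestive only, because fatigue can recover with rest and a true aftereffect may outlast the block. The check can indicate possible drift; it cannot remove it.

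### Recruiting 12 to keep 10 covers a dropout of 2 in 12 (16.7%), not the stated 20%, which would need 13

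*Combined protocol and SAP*

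**What the plan says.** Under Statistical considerations and Data Management, the Sample Size section bases the calculation on peak knee flexion angle, control against HWA walking. The inputs are given as "To detect a mean difference of 5 degrees with a standard deviation of 5 degrees", with a two-sided test at the 5% level, and the result is stated as "power of 80%, would require 10 participants". The next sentence reads: "To allow for a 20% dropout rate 12 participants will be recruited". The Study Summary also gives 12 subjects. The text does not say what the 20% is a percentage of.

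Two other statements bear on the consequences. The Sample Size section continues: "At the mid point of participant testing (6 participants) sample size will be recalculated and the sample adjusted if necessary". In the Testing Plan, the walking measurements belong to Data Set 3, which is collected in a single session, and "Group B participants will complete measures in Data Set 3 during the initial testing session". Group A does Data Set 3 in its final session.

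**The concern.** A reader takes a 20% dropout rate to mean that one in five of those enrolled may be lost and the study will still have the participants it needs. The number 12 does not deliver that. It is what results from adding 20% to the required 10, whereas an allowance for loss among those recruited divides the required number by the proportion expected to remain.

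The base of 10 has almost no slack, because it is the smallest number that reaches 80% power under the plan's inputs. The stated power and the stated allowance therefore hold together only up to 2 losses. The misstatement could be repeated in a report, or carried into the mid-point recalculation when a revised number is inflated for dropout.

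**Working it through.** **Inputs.** All come from the Sample Size section: mean difference 5 degrees, SD 5 degrees, two-sided 5%, power 80%, 10 required, 20% dropout, 12 recruited. The Data analysis plan names the paired t-test. The plan does not say which SD the 5 degrees is. I take it as the SD of the within-person differences, because that reading reproduces the plan's own number.

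**Step 1: reproduce the 10.** The standardised difference is d = 5/5 = 1. Power of the two-sided paired t-test comes from the noncentral t distribution with n − 1 degrees of freedom and noncentrality d√n:

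| Pairs | Power |
|---|---|
| 9 | 74.8% |
| 10 | 80.3% |
| 11 | 84.8% |
| 12 | 88.3% |

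Ten is the smallest n that reaches 80%, so the plan's figure is reproduced.

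**Step 2: reproduce the 12.**

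- Adding 20% to the required number: 10 × 1.20 = 12. This gives the plan's figure exactly.
- Allowing for 20% loss among those recruited: 10/(1 − 0.20) = 12.5, rounded up to 13.
- Check in the other direction: 12 × 0.80 = 9.6 expected completers, below 10; 13 × 0.80 = 10.4, above 10.
- Losses that 12 can absorb: 12 − 10 = 2, and 2/12 = 16.7%. A third loss is 3/12 = 25% and leaves 9 pairs, with 74.8% power.

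**Step 3: size of the effect if dropout really is 20%.** Each participant is treated as lost independently with probability 0.20. Mean power is the power at each possible number of pairs, weighted by its binomial probability.

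| Scenario | Chance of at least 10 pairs | Chance of fewer than 10 | Mean power |
|---|---|---|---|
| 12 recruited, every dropout loses the walking data | 55.8% | 44.2% | 77.1% |
| 13 recruited, every dropout loses the walking data | 74.7% | 25.3% | 81.1% |
| 12 recruited, all losses between sessions, 6 per group | 90.1% | 9.9% | 83.5% |

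In the last row only Group A can lose the walking comparison, because Group B has already completed it. The equal split is an assumption; the plan says only that allocation is by drawing from an envelope. At least 10 pairs then requires at least 4 of Group A's 6 to return.

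Against the 80% target, the shortfall with 12 is 80 − 77.1 = 2.9 points of mean power in the least favourable scenario, and there is none in the most favourable one.

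**The case against.** The best defence is that the figures agree on one reading: 10 plus 20% of 10 is 12, and the text never names the base of the percentage. The gap before rounding is half a person. A loss of 2.4 people cannot occur, and 12 does cover the nearer whole number, 2. The number is also provisional, since the sample is to be recalculated after 6 participants and may be adjusted. Group B gives its walking data in the first session, so some dropouts would cost the primary comparison nothing. Nor does 13 guarantee 10 pairs: under the least favourable scenario it still falls short about a quarter of the time.

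Most of this stands as a limit on how much the point matters. It rules out any claim that the trial is shown to be underpowered. It does not make the sentence correct. The plan speaks of a dropout rate, not of recruiting 20% extra, and nowhere defines the rate as a share of completers. Rounding 2.4 down to 2 is the 16.7% case. The recalculation might absorb a missing participant, but it is described without any rule for dropout, so it cannot be relied on to do so.

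**Conclusion.** The point holds and is minor. On the ordinary meaning of a dropout rate, 12 recruited does not allow for 20% loss at the stated power: it allows for 2 losses, 16.7%, and 20% would call for 13. The cost is at most about 3 points of mean power, and may be nothing, depending on when participants leave. The documents do not say when dropout is expected.

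The percentages for loss among those recruited follow from the plan's figures alone. The power figures also assume that 5 degrees is the SD of the paired differences, and the mean-power figures further assume independent losses at 20%. No test or estimand is affected.

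**What to change.** Keep 12 and replace the dropout sentence with wording such as: *Twelve participants will be recruited, which allows for loss of primary walking data in 2 participants (about 17%) at 80% power; power is about 75% if 3 are lost.* In the sentence before it, identify 5 degrees as the assumed SD of the paired differences, since the base of 10 depends on that reading.

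If the sponsor wants to hold to a 20% allowance, the consistent number is 13, at the cost of one more participant. The rewording adds no participants and leaves the analysis unchanged.
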